8. CONSENT PROCESS

This study includes 2 documents: 1) Adult Information Sheet, and 2) Legal Guardian Permission.

Interested adults with FASD will be directed to the link to the study REDCap Screening Module from recruitment materials. Participants will first be given the option whether they would like to learn about the study by 1) reading the Study Information Sheet or 2) view a video summarizing this information. After reviewing either option, they will be asked several questions assessing their understanding of the information. All participants will be given the option to download a copy of the Information Sheet for their records. This will also allow them sufficient time to review the form and discuss it with other people in their life if they choose. There will also be a section where they can indicate if they have any questions, and our study coordinator will call them. The study coordinator's contact information will also be presented if participants want to contact the coordinator with questions while reading the document/watching the video. The study coordinator will document contact in the study contact log in REDCap. Additional items will screen for eligibility and obtain contact information. There will also be a question about whether they have a parent/legal guardian, so we can contact that person if needed to obtain permission. Given the broad range of functioning within this population, the Information Sheet language was adapted in some places to be at a lower reading level. Headings were also added, similar to the Adolescent Assent template.

We request a waiver for documentation for the Study Information Sheet. The primary identifying information collected as part of this study are participant contact information in the REDCap Screening Module. This contact information would allow us to contact participants in several anticipated scenarios, such as: if they indicate they have questions about the study, they provide inconsistent information we need to clarify (e.g., country they live in vs. response

Page 4 of 13

for "live in UK or EU"), or to send them surveys or schedule interviews. This contact information would also allow us to remove or change participant data as requested by a participant under GDPR requirements if needed. Identifying information will be stored separately from other de-identified data sources. In addition, this study is minimal risk and involves procedures (e.g., survey responses, app usage) for which written consent is not normally required outside the research context. There is also not an easy way to verify participant identify for written eConsent without creating an additional step for participants involving communication with research staff through another method (e.g., email, phone).

After reviewing the information sheet, participants will be directed in REDCap to answer screening questions to assess eligibility for the study (see Screening Form). If eligibility criteria clearly aren't met (e.g., out of age range, no smartphone, etc), participants will be informed immediately that they aren't eligible and the module will end. Screening data will be maintained for ineligible participants to aid in clinical trial reporting requirements (e.g., documenting numbers screening, eligible vs. ineligible, and reasons).

For adults who appear to meet criteria or in cases where they answer "unsure" for any of the questions, further contact information will be gathered. Contact information will also include necessary variables to generate their "globally unique identifier" (GUID), which is used in other CIFASD studies and required for the NIAAA-Data Archive (https://nda.nih.gov/s/guid/nda-guid.html).

Legal Guardians: For legal guardians, written permission will be obtained using REDCap's eConsent signature field. A study team member will contact the legal guardian based on information provided by the participant in their survey. During this contact the study team will provide the legal guardian a passcode to enter when completing the eConsent to serve as verification of their identity. The legal guardian will then select "Next Page" and a read only copy of the consent will be generated that they can review, download, and/or print. At the bottom of the page, they will need to select "I certify that all the information in the document above is correct, and I understand that signing this form electronically is the equivalent of signing a physical document." Once this is selected, they will be able to submit the signed consent form.

Upon completion of the permission survey, a static copy of their responses in the form of a consent-specific PDF will be stored in the project's File Repository in REDCap (to allow for versioning). The e-Consent Framework in REDCap also records their IP address and displays this information in the file repository in order to help regulate potential duplicate forms from a single IP address. A PDF file of the completed consent form will be available for download by the user. The PDF can also be emailed to legal guardians or printed/sent to them in the mail on request if they are unable to open or save a copy electronically on their device.

Participant completion of the study permission document also triggers an automatic notification to the study coordinator, who will log-in to REDCap and review the consent. She will then add her name and date to the eConsent document. However, the date study staff sign the eConsent may differ from that of the participant; for example, if the participant completes the forms on a weekend. The coordinator will also document the date of this review in the

Page 5 of 13

study database and download a copy of the consent form to maintain in study records. Next the coordinator will review screening responses and demographic variables to assess eligibility and will document this in the study database.

This study is funded by the National Institute of Health (NIH). A Certificate of Confidentiality is automatically included as part of the notice of award. Language regarding the Certificate of Confidentiality is included in the consent documents.

Due to an increase in fraudulent participants across studies, we have developed a lab-wide guide to minimize, detect, and systematically manage fraudulent participants (see uploaded). For this study (as of June 2023), if "red flags" (e.g., common email formula, unusual emails; see lab-wide guide for other examples) are identified by research staff, they will follow lab scripts to withdraw the participant.

9. STUDY PROCEDURES

The project research assistant will track participants in REDCap once enrolled and will facilitate timely completion of research assessments. All participants will be encouraged to complete assessments, regardless of their level of engagement with the My Health Coach app. Actual user data from the app (whether minimal or extensive) will be important in addressing study aims.

After informed consent, participants will be asked to complete a set of baseline surveys (see details on the assessment battery below). To be most sensitive, given the unique neurobehavioral profiles of participants, administration will be flexible based on participant needs and can include surveys completed independently online, over the phone or Zoom with research staff, or through the mail. Afterwards, they will be provided information on how to install the app on their phones. Study staff will be available to troubleshoot problems with installation or app use. After 6 weeks, all participants will be re-contacted to complete follow-up surveys. User implementation data will be gathered through the app. To further assess acceptability, satisfaction, and barriers and facilitators of app use, the study research assistant will complete qualitative interviews with participants over HIPAA-complaint Zoom or telephone. Interviews will be recorded and later transcribed verbatim.

Study Assessment Battery

Measure	Baseline	6-Week
		Follow-up
Quality of Life: Personal Well-being Index – Intellectual	X	X
Disability Version		
Self-Determination: The Basic Psychological Need	X	X
Satisfaction and Frustration Scale		
Self-Management	X	X
Barriers to Healthcare Checklist	X	
FASD Education	X	
Basic Demographics	X	
Acceptability: Theoretical Framework of Acceptability		X
measure		

Page 6 of 13

Qualitative Interview on User Experience		X
--	--	---

Qualitative Interview. The semi-structured questioning route will cover the following topics: 1) overall impressions of My Health Coach; 2) experience using the app (both facilitators and barriers of use); and 3) perceived impact on their health and well-being. Interviews are expected to last about 30 minutes.

My Health Coach app. The My Health Coach app is designed to offer adults with FASD evidence-based education about their condition and tools to promote their own self-management and health advocacy goals. It uses a chatbot interface to engage with users and help navigate through the app features. The user will be able to customize their chatbot as well as their own avatar to ensure they feel comfortable while using the app. Key features include a daily check-in, which records mood, physical health symptoms, sleep quality, and positive activities completed each day. Daily answers can be referred back to as needed. The app also includes a tracker the user can cusstomize to track things such as medication or daily tasks. Next, the app will also include a library where users can access evidence-based factsheets on their condition and strategies to aid with condition management. Lastly, the app will send a daily message notification. These will include strategies, FASD facts, and positive affirmations.

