4. STUDY DESIGN

Page 2 of 13

This feasibility study will use a single group design with assessment timepoints prior to the receipt of the app and 6-weeks later. Primary outcomes assessed will include quality of life, self-determination theory constructs (i.e., autonomy, competence, relatedness), self-management, and barriers to care. Acceptability of the app and trial procedures will also be assessed at the 6-week timepoint.

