5. SUBJECT POPULATION

The study population will include adults (18+) with FASD. We will aim to enroll 48 adults with FASD to achieve a final sample of 40 participants with complete data. Additional participants will be enrolled if attrition is greater than anticipated.

In prior studies conducted by the ALC, 45% of participants were from Canada, 40% from USA, 9% European countries, 5% Australia / New Zealand, and 2% African countries. As such, we anticipate the vast majority of participants in our study will also be from the US and Canada. However, some will likely come the EU and UK and fall under GDPR requirements. A "Notification for Collection and Use of Personal Data" is included in the REDCap Screening Module immediately after the Study Consent Form to inform all participants from the EU or UK about compliance with GDPR requirements.

It is also possible that some adults with FASD will have legal guardians due to decisional impairment (in either specific or global domains). For these adults to participate, their legal guardian would also need to review the study consent form and provide written permission. Legal guardianship in Canada is rare but is used sometimes for adults with FASD in the US. A question in the screening module asks about legal guardianship. For those adults who indicate they have a legal guardian, our research team will contact that person to go over the permission form and obtain the needed signature through REDCap.

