16. PRIVACY AND CONFIDENTIALITY OF SUBJECTS AND RESEARCH DATA

All data will be used solely for research purposes and will be securely locked in designated file cabinets, URMC managed Box folder dedicated to project, Project REDCap database, and an encrypted, HIPAA-complaint Cloud database (AWS; for data collected via the app; see above). Identifying information will be stored separately from other data, which will be stored by research ID number (GUID). Multiple procedures will be implemented to protect participant data collected through the app, which are further detailed in the section "Protections Against Risks" and Data Security Assessment form. Only senior key personnel and project research staff will have access to the data.

The following table summarizes the project data flow. MHFC IT will set up and manage permissions for URMC Project Box folder. Only project staff will have access to REDCap and Box folders. [name] will coordinate with the CIFASD5 Coordinating Center to facilitate required data uploads to NIAAA-Data Archive as required by the grant for eligible de-identified data (pre-post surveys; all other data exempt).

Data Element	How Data	Where Data is	How Data is Managed
	Collected	Stored	
Information	REDCap	REDCap, Back-ups	MHFC IT; Project Staff
Sheet,		URMC Box	
Screening			
Survey,			
Contact			
Information			
Legal Guardian	REDCap	REDCap, Research	MHFC IT; Project Staff
Permission		staff signed copy of	
Form		permission form on	
(eConsent)		URMC Box	
Baseline (T1)	REDCap	REDCap, Back-ups	MHFC IT; Project Staff;
Surveys		URMC Box,	CIFASD5 Coordinating
		CIFASD/NIAAA-DA	Center
6-week	REDCap	REDCap, Back-ups	MHFC IT; Project Staff;

Page 9 of 13

Follow-up (T2)		URMC Box,	CIFASD5 Coordinating
Surveys		CIFASD/NIAAA-DA	Center
Follow-up	Zoom, back-	URMC Box	MHFC IT; Project Staff;
Interview	up audio		Audio/video data is
	recording		transcribed verbatim;
			audio/videos deleted once
			transcript verified
My Health	User device	URMC-managed	Access is restricted to
Coach App	synchronized	account on AWS	authorized individuals and
usage data and	with AWS		every access to the data will
User's inserted			be logged, data is encrypted
data			in transit and at rest. AWS
			account is set up in
			compliance with UR/URMC
			policies and monitored by
			Lacework.

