17. DATA ANALYSIS PLAN

Pre-Post Intervention Outcomes. Descriptive statistics, reliability indices, and pre-post effect sizes (Cohen's d) will be calculated for baseline and follow-up quantitative measures and user implementation data. Data will provide useful estimates to inform larger randomized control trials of the app. Data will also guide further app refinements.

Qualitative Interviews. Data will be analyzed thematically to understand users' experiences with the My Health Coach app and research trial. The purpose is to inform further app development. Thematic analysis focuses on identifying patterns or themes within the data. Consistent with the approach advocated by Miles, Huberman, and Saldana [15], research team members will first familiarize themselves with the data, iteratively reviewing each transcript, and independently assigning initial codes ("first-level coding"). The team will then come together and discuss, operationalize, and refine each code. We will also generate "second-level codes" which consider categories or deeper meanings among first-level codes. During this process we will examine interrelationships and networks among codes and build a preliminary thematic framework. Transcripts will then be recoded and codes refined through further discussion and consensus, as needed. Participant and group "fit" with the framework will also be assessed, with confirmatory and disconfirmatory evidence for the model examined. Participant matrices may also be utilized to examine variance in themes across participants and key demographic factors, pre-post intervention change, or usage patterns.

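### Does flexible survey mode, with no stated rule for matching or recording it at week 6, undermine the pre-post effect sizes?

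*Combined protocol and SAP*

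**What the plan says.** Section 9 (Study Procedures) places the rule on mode directly after the sentence on baseline surveys: "administration will be flexible based on participant needs and can include surveys completed independently online, over the phone or Zoom with research staff", or by mail. It gives the participants' neurobehavioral profiles as the reason. For the second time point it says only: "After 6 weeks, all participants will be re-contacted to complete follow-up surveys". The assessment battery in the same section marks three measures at both visits: quality of life, self-determination and self-management. A pre-post effect size can be computed only for these.

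On record keeping, section 9 states: "The project research assistant will track participants in REDCap once enrolled and will facilitate timely completion of research assessments". Section 16 (Privacy and Confidentiality) has a data-flow table that gives REDCap as the collection route for both the baseline and the six-week surveys. Neither place names survey mode as a data item. The contact log in section 8 concerns questions raised at the consent stage.

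On design and analysis, section 4 states: "This feasibility study will use a single group design with assessment timepoints prior to the receipt of the app and 6-weeks later". Section 5 sets the size: "We will aim to enroll 48 adults with FASD to achieve a final sample of 40 participants with complete data". Section 17 says that "pre-post effect sizes (Cohen's d) will be calculated for baseline and follow-up quantitative measures and user implementation data", and adds: "Data will provide useful estimates to inform larger randomized control trials of the app". It plans no hypothesis test and makes no use of mode.

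**The concern.** People may answer questions about well-being or self-management differently when a staff member asks them than when they complete a form alone. If a participant completes the baseline survey online and the six-week survey by telephone, the change score mixes true change with a mode effect. A randomized comparison would largely cancel such an effect between arms, but this study has one group and nothing to cancel it.

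A one-way drift is conceivable. Staff re-contact everyone at six weeks, the research assistant helps to get assessments finished on time, and interviews by Zoom or telephone fall at the same visit. Late online surveys might therefore be completed with staff. If that raised or lowered answers, d would shift by an amount that no confidence interval reflects. Unless mode had been logged at both visits, nobody could check it afterwards. Because the study's data are meant to inform later randomized trials, a shifted d could be carried forward.

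**Working it through.** **Inputs from the documents.** 48 enrolled and 40 with complete data (section 5). No attrition rate is stated; the two figures imply 1 − 40/48 = 16.7%. The documents give no SD, pre-post correlation, mode effect or switching rate.

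**Assumed inputs.** Mode effect δ of 0.2 to 0.4 SD, with 0.1 SD as a smaller value; pre-post correlation r of 0.5 or 0.8; d standardised by the baseline SD; a mode effect that is the same for everyone.

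**Bias.** Bias in d = (share switching one way − share switching the other way) × δ.

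- Balanced switching: 0.
- Net 5% (2 of 40): 0.05 × 0.2 = 0.01 to 0.05 × 0.4 = 0.02.
- Net 25% (10 of 40): 0.25 × 0.2 = 0.05 to 0.25 × 0.4 = 0.10. With δ = 0.1 it is 0.025.

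A simulation with no true change (n = 40, 20,000 runs, r = 0.5) gave a mean d of 0.051 and 0.103 for the net 25% case. That confirms the formula but says nothing about whether the inputs are realistic.

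**Sampling error.** For d near 0, SE = √(2(1 − r)/n).

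- r = 0.5: √(1.0/40) = 0.158, 95% half-width 1.96 × 0.158 = 0.31.
- r = 0.8: √(0.4/40) = 0.100, 95% half-width 0.20.

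**Bias relative to SE.**

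| Net switch | r = 0.5 | r = 0.8 |
|---|---|---|
| 5% | 0.06 to 0.13 SE | 0.10 to 0.20 SE |
| 25% | 0.32 to 0.63 SE | 0.50 to 1.00 SE |

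**Net switch needed for a bias of one SE** (SE/δ).

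- r = 0.5: 0.158/0.4 = 40% to 0.158/0.2 = 79%, about 16 to 32 of 40.
- r = 0.8: 0.100/0.4 = 25% to 0.100/0.2 = 50%, 10 to 20 of 40.
- With δ = 0.1, all 40 would have to switch at r = 0.8, and even that would not be enough at r = 0.5.

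**Choice of standardiser.** Section 17 says only Cohen's d. If d is divided by the SD of change instead, balanced switching is not wholly neutral when there is true change. At r = 0.8, with 25% switching in total and δ = 0.4, the variance of change rises from 0.40 to 0.40 + 0.25 × 0.4² = 0.44. Since √(0.40/0.44) = 0.953, d shrinks by about 5%, which is negligible here.

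**What a same-mode analysis could show.** Suppose 30 of 40 pairs kept one mode. The SE at n = 30 is 0.183 (r = 0.5) or 0.115 (r = 0.8). The SE of the difference between the full-sample and same-mode d is √(SE₃₀² − SE₄₀²) = 0.091 or 0.058. A bias of 0.05 to 0.10 is then 0.5 to 1.1 SE or 0.9 to 1.7 SE, so the comparison would usually settle nothing.

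**The case for a change.** The best case for a change has three parts.

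First, the omission is real. No section states a matching rule or names mode as a recorded item at either visit, and a systematic shift, unlike sampling error, stays hidden in the interval. As an illustration, suppose the true effect is 0.3, the test is two-sided at 5% with 80% power, and the pilot d is used directly as the between-arm effect. The correct size is 175 per arm. A d inflated by 0.06 gives 122 per arm and 65% power; one inflated by 0.10 gives 99 per arm and 56% power.

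Second, section 2 says that trial procedures are themselves under test. How many participants need a telephone call, and whether that changes by week 6, would be useful to the next trial's planners.

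Third, a field in REDCap costs almost nothing.

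The first part stands as a description of the text. It is an argument from silence, though: the REDCap forms are not among the documents, and mode may well be logged. The illustration assumes a use of d that section 17 does not propose. Even on that assumption, an inflation of 0.10 is one SE at r = 0.8, so chance alone would often do as much damage in a pilot of 40.

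The second and third parts make logging mode sensible practice, but they do not show that the planned analysis is unsound without it. Recording mode would reveal a drift without removing it, and counting switches cannot size a bias when the mode effect is unknown. Asking for the same mode wherever the participant can manage it differs little from choosing mode by need, which the protocol already does.

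**Conclusion.** No change to the plan is needed. The protocol is silent on matching and recording mode, and it is unclear whether the flexible modes extend to week 6. This is a gap in operational detail that the study team can fill sensibly. Choice by need probably keeps many participants in one mode, and only a net one-way movement shifts a d standardised by the baseline SD. Under the assumed mode effects of 0.2 to 0.4 SD, a net switch of up to 25% leaves the bias at or below one SE, and 25% to 79% would have to move one way to reach one SE. Smaller mode effects make it less still.

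The flexibility is a fair trade-off: it helps adults with FASD to complete both surveys, at the price of a small possible bias in descriptive estimates from a feasibility study. The conclusion rests on assumed mode effects, correlations and switching shares, since the documents supply none. It would be weaker if a large share of participants moved from self-completion to staff administration between visits, which nothing in the protocol indicates.

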10. AUDIO/VIDEO RECORDINGS

Qualitative interviews will be recorded using HIPAA-complaint Zoom with a digital recorder audio back-up. Research staff will be at Mt. Hope Family Center when completing interviews, using UR computers. Recordings will uploaded from the local machine as soon as possible to a URMC Box folder for this project managed by the IT team at Mt. Hope Family Center. Only research staff involved on this project will have access to recordings. Recordings will then be transcribed verbatim by research staff. After all transcripts have been rechecked, audio and video recordings will be deleted.

